3.1 Dosage and Administration Schedule

Copanlisib is given intravenously at a dose of 60 mg over 1 hour on day 1, 8, and 15 in a 3 week on/1 week off schedule. Each cycle is 28 days and cycles are repeated until progression. Please see Section [3.5](#) for dose modifications.

The use of corticosteroids as antiemetics prior to copanlisib administration is not allowed. After administration, flush the line with 0.9 % sodium chloride to ensure complete dose is given. No IV glucose preparations should be administered on the days of infusion.

Rev. Add16

Blood pressure measurement on treatment days

Blood pressure will be measured prior to each copanlisib dose (no more than 4 measurements) until there are two consecutive results < 150/90 mmHg with at least a 15 min interval between the measurements to be able to start the infusion of the study medication (pre-dose). The investigator can consider a medical intervention to maintain blood pressure in values appropriate for infusion. The investigator must delay the infusion until blood pressure values are below 150/90.

On copanlisib infusion days, blood pressure will be measured at pre dose, 30 min after the start of infusion, right after the end of infusion; and 1 h and 2 h after the end of copanlisib infusion.

NOTE: Time window of \pm 10 min is allowed for all post dose blood pressure measurements.

Rev. Add16

Recommendations on meal timing on copanlisib infusion days

Because of an inhibitory effect on PI3K α -isoform, which is implicated in insulin metabolism, copanlisib infusions could be associated with temporary increase in blood glucose. Consuming meals in close proximity to copanlisib infusion may exacerbate a glucose level increase.

On infusion days a low carbohydrate diet is recommended, the timing and content of meal intake and additional glucose testing (if clinically indicated) is managed and monitored by the investigators based on glucose response patterns during prior treatment days.

All glucose measurements done at the site, oral glucose lowering medication and/or insulin administration, if applicable, pre-dose fasting/non-fasting status and meal intake timing on infusion days should be documented.

Rev. Add16
Rev. Add25

Pre-dose glucose levels

Period	Pre-dose glucose levels
Day 1 of cycle 1	< 160 mg/dL (fasting) < 200 mg/dL (non-fasting)
Day 1 of subsequent cycles	< 160 mg/dL (fasting) < 200 mg/dL (non-fasting)
Days 8 and 15 of each cycle	< 160 mg/dL (fasting) < 200 mg/dL (non-fasting)

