3.5 Dose Modifications

All toxicity grades below are described using the NCI Common Terminology Criteria for Adverse Events (CTCAE) version 5.0.

All appropriate treatment areas should have access to a copy of the CTCAE version 5.0. A copy of the CTCAE version 5.0 can be downloaded from the CTEP website

(http://ctep.cancer.gov/protocolDevelopment/electronic_applications/ctc.htm).

The side effects observed with copanlisib (BAY 80-6946) are consistent with those observed with other PI3K inhibitors.

Copanlisib will be administered at fixed dose (60 mg) intravenously on Days 1, 8, and 15 on a 28-Day cycle. Copanlisib dose reduction instructions provided in **Table 1** serve as guidelines to allow ongoing treatment for patients without signs or symptoms of progression while monitoring patient safety. If there is need to interrupt dosing for grade 3/4 toxicity, then there will be a dose reduction as per the table below, once toxicity improves to grade 1 or baseline. Selected toxicities / adverse events of interest for copanlisib include hyperglycemia, rash, hypertension, diarrhea.

Table 1 Overall Dose Modification Guideline for Copanlisib (BAY 80-6946)-Related Adverse Events

	Copanlisib
Starting dose	60 mg
First reduction	45 mg
Second reduction	30 mg

Dose may be suspended for up to 4 weeks due to toxicity. Patients requiring treatment to be held for >4 weeks will be taken off treatment. If treatment held for laboratory abnormality, recheck labs in one week. No dose reduction is allowed for patients treated at a dose 30 mg of copanlisib – if there is an indication for further dose reduction, the patient must permanently discontinue copanlisib. Dose re-escalation is not allowed after a dose reduction.

Rev. Add16

Dose Modification rules for transient post-infusion hyperglycemia

Patients who develop post-infusion glucose increases of grade 2 after study drug administration may continue treatment. However, the next infusion must be delayed until the patient's pre-infusion glucose levels return to < 160 mg/dL (fasting) or < 200 mg/dL (non-fasting). Guidelines for the management of transient glucose increases are given in [Appendix III](#). Continuing occurrence of post-infusion blood glucose increases of grade ≥ 3 despite optimal glucose lowering therapy after 2 infusions of copanlisib, will require dose reduction by one dose level.

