- Further dose reduction (**where appropriate per study design/population**) is allowed as long as discontinuation criteria was not met.
- Dose re-escalation is allowed when a patient has achieved controlled glucose levels per investigator's judgment.
- Occurrence of post-infusion non-life threatening hyperglycemia requiring interventions at the protocol defined lowest dose level despite optimal

glucose lowering therapy (after at least one cycle of treatment) requires permanent discontinuation of the study drug.

- Occurrence of post infusion life-threatening copanlisib related hyperglycemia requires permanent discontinuation of the study drug

Management of Hyperglycemia

Metformin is the first antihyperglycemic medication of choice because of the lower risk of hypoglycemia with this agent. Because metformin in some patients may also cause diarrhea and can be poorly tolerated, other antihyperglycemic medications such as sulfonylureas (e.g. glimepiride, glipizide) can be used. Extra caution should be used with other drugs such as sulfonylureas because of the increased risk for hypoglycemia with these agents. Consultation with an endocrinologist can be helpful in managing hyperglycemia.

Insulin should only be used for patients with persistent, symptomatic hyperglycemia. It should not be used to lower glucose level on the day of infusion due to the risk of hypoglycemia. On treatment days, it is best to hydrate the patient and not give insulin to reduce glucose levels to meet study treatment criteria.

Management guidelines for fasting patients with hyperglycemia are listed below in Table 2.

Table 2: Management of Hyperglycemia

Grade	Intervention	Dose Adjustment
1	Initiation of an oral anti-hyperglycemic agent (e.g., metformin) and additional glucose monitoring should be considered.	No change.
2	Initiation or increased dose of an oral anti-hyperglycemic agent (e.g., metformin) and additional glucose monitoring should be considered.	Dosing with copanlisib may either be held or continued per Investigator evaluation.

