3, asymptomatic	Patient should be managed as per standard care, including implementation of additional glucose monitoring and initiation and/or increase of anti-hyperglycemic therapy (e.g., metformin).	Consideration should be given to suspend copanlisib dosing until the hyperglycemia resolves to Grade \leq 2. Dosing with copanlisib may resume at the same dose level or at one dose level lower as outlined in Table 1 and after discussion with the Study Principal Investigator.
3, symptomatic (e.g., blurred vision, frequent urination, excessive thirst) or grade 4	Patient should be managed as per standard care, including implementation of additional glucose monitoring and initiation and/or increase of anti-hyperglycemic therapy	Copanlisib dosing should be suspended until the hyperglycemia resolves to Grade \leq 2. The patient will be discontinued from the study if such therapy fails to control their hyperglycemia. Dosing with copanlisib may otherwise resume at one dose level lower as outlined in Table 1.

*Based on fasting glucose level

Management of Rash

Treatment related rash has been reported with copanlisib. While most were CTCAE v3.0 Grade 1 or Grade 2 in severity, few patients experienced Grade 3 rash. Rash is generally macular or maculo-papular with or without pruritus, with some having developed desquamation. Patients with severe rash should be monitored for associated signs and symptoms, such as fever and hypotension that may be suggestive of a systemic hypersensitivity reaction. For severe rash, hold all study treatment until Grade ≤ 1 (see Table 3 below), and patients should be treated with supportive therapy per standard of care. Use of topical antihistamine, as well as topical or systemic corticosteroids, may be considered. There is no evidence for a phototoxic potential of copanlisib.

Table 3: Dose Delay and Modification Guidelines for Rash

Grade	Intervention	Dose Adjustment
Grade 1	Consider prescribing topical corticosteroids ^a	Continue dosing at current dose and monitor for change in severity.
Grade 2	Consider treatment with supportive therapy (e.g., topical or oral corticosteroids ^{a, b}).	Consider holding copanlisib or reducing to the next lower dose if rash is troublesome.

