Appendix III

Management of Transient Glucose Increase On the Day of Copanlisib Infusion

Criteria	Recommendation	Suggested Treatment
Asymptomatic glucose increases $\leq 250\text{mg/dL}$	Does not generally require treatment with glucose lowering medication.	None
Asymptomatic glucose increase $> 250\text{ mg/dL}$	
 Should have repeated laboratory glucose determination. If the repeated glucose value is decreasing, the glucose may be followed without glucose lowering medication treatment if hydration status is normal as clinically assessed. Consultation with endocrinologist is recommended 	
 Hydration if appropriate When planning next infusion consider prophylaxis with oral glucose lowering medication
Symptomatic or persisting glucose increases $> 250\text{mg/dL}$	
 Hydration status should be clinically assessed. If clinical assessment is consistent with dehydration, fluids should be given as clinically appropriate (orally or IV). Laboratory test confirming increase should be repeated. If the repeated glucose value is persistent and/or patient is symptomatic and/or the hydration status indicates the need for hydration, glucose lowering medication should be administered. Prompt input from a diabetes specialist should be obtained. 	
 Hydration if appropriate Rapid/ short acting insulin may be given for glucose persisting at $> 250\text{ mg/dL}$, or if the patient is symptomatic during the infusion day. Rapid/short acting insulin According to the institution sliding scale coverage of glucose persisting at $> 250\text{ mg/dL}$ is recommended, with oral or IV hydration as clinically appropriate When planning next infusion consider prophylaxis with oral glucose lowering medication

**Molecular Analysis for Therapy Choice (MATCH)
MATCH Treatment Subprotocol Z1G: Copanlisib, PTEN Loss**

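### Section 3.5 and Appendix III give opposing instructions on insulin on the day of copanlisib infusion

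*Protocol*

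**What the plan says.** Four places in the Protocol bear on insulin.

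- **Section 3.5, Management of Hyperglycemia.** "Insulin should only be used for patients with persistent, symptomatic hyperglycemia". The next sentence reads: "It should not be used to lower glucose level on the day of infusion due to the risk of hypoglycemia". A third sentence prefers hydration on treatment days over insulin given to bring glucose within the limits for dosing.
- **Section 3.5, rules for transient post-infusion hyperglycemia.** "Guidelines for the management of transient glucose increases are given in" Appendix III. The appendix is therefore an operative part of the plan.
- **Appendix III**, whose title confines it to the infusion day. In the row for symptomatic or persisting increases above 250 mg/dL: "Rapid/ short acting insulin may be given for glucose persisting at" more than 250 mg/dL, "or if the patient is symptomatic during the infusion day". The same cell recommends sliding-scale insulin coverage when glucose persists above 250 mg/dL.
- **Section 3.1**, on infusion days, asks sites to document "oral glucose lowering medication and/or insulin administration, if applicable".

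Two further rules matter for the secondary points. A bullet in Section 3.5 states: "Occurrence of post infusion life-threatening copanlisib related hyperglycemia requires permanent discontinuation of the study drug". Table 2, in the row for symptomatic grade 3 or grade 4, says to suspend until grade 2 or lower and to stop if therapy fails; then: "Dosing with copanlisib may otherwise resume at one dose level lower as outlined in Table 1".

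**The concern.** Section 3.5 advises against insulin on the infusion day and gives hypoglycaemia as the reason. Appendix III allows it on that day and, in one situation, recommends it. The conditions differ as well: Section 3.5 asks for persistence *and* symptoms, Appendix III for persistence *or* symptoms. No sentence says which text governs.

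The situation is not remote. Sections 1.2.3 and 1.3 put the glucose peak 5 to 8 hours after treatment, that is, on the infusion day. Section 1.3 reports hyperglycaemia in 63.2% of patients in Study 12871, and at grade 3 in 33.3% of 57. Section 2.1.9 admits patients with type I or II diabetes if HbA1c is at most 8.5%, and the Section 3.5 insulin sentences make no exception for them. Patients in the same state could therefore be handled in opposite ways at different sites, on a matter where the protocol itself names a hazard.

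**Working it through.** The protocol states no figure to reproduce. The check sets the passages side by side and counts the situations in which they differ.

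**Inputs**

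- Section 3.5, infusion-day sentence: insulin not to be used to lower glucose that day; no exception written.
- Section 3.5, preceding sentence: insulin only if persistent *and* symptomatic.
- Appendix III: insulin may be given if persisting above 250 mg/dL *or* symptomatic; sliding-scale coverage recommended if persisting above 250 mg/dL.

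**Situations.** For infusion-day glucose above 250 mg/dL: {persisting, not} × {symptomatic, not} = 2 × 2 = 4.

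| State | Appendix III | Section 3.5 as worded | Section 3.5 if the infusion-day sentence is pre-dose only |
|---|---|---|---|
| Persisting, symptomatic | allowed and recommended | not to be used | allowed |
| Persisting, asymptomatic | allowed and recommended | not to be used | not allowed |
| Not persisting, symptomatic | allowed | not to be used | not allowed |
| Not persisting, asymptomatic | no insulin advised | not to be used | not allowed |

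**Counts**

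- Appendix III allows insulin in 3 states.
- Section 3.5 as worded allows it in 0. Difference: 3 − 0 = 3 of 4. In 2 of these a recommendation meets advice to withhold; in 1 a bare permission does.
- Section 3.5 on the pre-dose reading allows it in 1. Difference: 3 − 1 = 2 of 4. In 1 of these (persisting, asymptomatic) Appendix III recommends insulin; in the other it only permits it.

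**Secondary overlaps (lower confidence)**

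- *Discontinuation.* The Section 3.5 bullet ends treatment permanently after life-threatening post-infusion hyperglycaemia. Table 2, based on fasting glucose, allows restart one dose level lower after grade 4. One patient can meet both descriptions. The protocol does not say how life-threatening relates to grade 4.
- *Restart.* The opening of Section 3.5 says that, after interruption for grade 3 or 4 toxicity, dosing resumes at a reduced dose once toxicity is at grade 1 or baseline. Table 2 allows restart at grade 2 or lower and, after asymptomatic grade 3, at the same dose. No precedence is written.

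**The case against.** The strongest reply is that the infusion-day sentence concerns insulin given before dosing. The sentence after it speaks of meeting the treatment criteria, which fits the pre-dose glucose limits in Section 3.1 (below 160 mg/dL fasting, below 200 mg/dL non-fasting). Table 2 in the same subsection is for fasting patients, and post-infusion rises have their own subsection that points to Appendix III. This is a plausible account of the intent. But the limit is inferred: the sentence carries no such restriction, and the reason it gives is general. Even if the limit is granted, the sentence before it still demands persistence and symptoms together.

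It can be answered that Section 3.5 sets no threshold or time frame for persistence, so the word may not mean there what it means in Appendix III. That is true, and the 2-of-4 count assumes a common meaning. Yet Section 3.5 restricts insulin without qualification, so the mismatch goes away only if a scope is read into it.

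Three other points stand in part:

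- A permission and advice to withhold can both be honoured by withholding. A site is caught between opposing advice only where Appendix III recommends insulin, that is, when glucose persists.
- The Section 3.1 documentation line is weak support, because diabetic patients may be on insulin anyway. The conclusion does not need it.
- The secondary overlaps may be settled by reading the specific rule over the general, or the fasting rule apart from the post-infusion one. They are ambiguities, not proven contradictions.

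**Conclusion.** The concern holds. Two current passages give opposing advice on insulin on the infusion day: they differ in 3 of 4 situations above 250 mg/dL as worded, and in 2 of 4 on the reading most favourable to the plan that was tested. The counts assume that persistent and persisting mean the same in both places. They measure how far the wording diverges, not how many patients are affected: the document gives no rate of glucose above 250 mg/dL, or of grade 4 hyperglycaemia, at the 60 mg flat dose, and the Study 12871 rates do not supply one. No endpoint or sample size is affected. It must nonetheless be corrected, because the conflict concerns a safety instruction for an expected effect of the drug. Confidence is high for the insulin conflict and lower for the discontinuation and restart overlaps.

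**What to change.** Issue an addendum that reconciles the Section 3.5 narrative, its bullets and Table 2 with Appendix III. It should:

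1. give one statement on infusion-day insulin: whether it may be given, whether the rule differs before and after dosing, and whether persistence and symptoms are both required or either suffices, with persistence defined;
2. say how life-threatening hyperglycaemia relates to grade 4, and which passage governs permanent discontinuation;
3. say which passage governs the grade and dose at restart after interruption for hyperglycaemia.

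Which clinical rule to adopt is for the sponsor; this review proposes none. The cost is a wording addendum and a notice to sites, with no effect on sample size.

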Grade 3 or 4	Consider treatment with supportive therapy (e.g., topical or oral corticosteroids ^{a, b}). Consider dermatological consultation. Consider obtaining photographs of rash if permitted by local regulations.	Hold all study treatment until Grade ≤ 1 . For Grade 3, restart copanlisib at the next lower dose upon discussion with Overall Principal Investigator, or permanently discontinue treatment. For Grade 4, permanently discontinue treatment.

a Suggested topical steroids include, hydrocortisone 2.5% to face twice daily, triamcinolone 0.1% or fluocinonide 0.1% cream to body bid.

b Suggested oral steroids include methylprednisolone dose pack or prednisone 60 mg daily followed by a taper (e.g., 60 mg \times 2 days, 40 mg \times 2 days, 20 mg \times 2 days, etc.).

Management of Hypertension

Patients receiving copanlisib who have experienced hypertension and blood pressure should be monitored at each visit. In subjects with an initial BP reading within the hypertensive range, a second reading should be taken at least 2 minutes later, with the two readings averaged to obtain a final BP measurement.

For patients who develop HTN or worsening HTN during study treatment, antihypertensive medication should be initiated or optimized to achieve target blood pressure before interruption or dose reduction of the study treatment at the discretion of the investigator. If hypertension is persistent despite adequate anti-HTN therapy including titration of anti-HTN medication or introduction of additional anti-HTN medications, dose interruption, reduction or discontinuation is recommended. If Grade 4 HTN develops, permanently discontinue treatment. Patients with prior history of hypertension (on anti-hypertensive agents) should monitor/record their BP at home while on copanlisib.

It is important that patients with pre-existing arterial hypertension adhere to their regular medication schedule and take their usual doses on the days of study drug infusion.

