	
 - Persistent hypertension: Hypertension detected in two separate readings during up to three subsequent visits. - Well-controlled hypertension: Blood pressure of SBP \leq 150 mmHg and DBP \leq 90 mmHg in two separate readings during up to three subsequent visits. - Symptomatic hypertension: Hypertension associated with symptoms (e.g., headache, light-headedness, vertigo, tinnitus, episodes of fainting) that resolve after the blood pressure is controlled within the normal range. - Asymptomatic hypertension: SBP $>$ 150 mmHg and/or DBP $>$ 90 mmHg in the absence of the above symptoms. 		
(Scenario A)	
 • Asymptomatic and persistent SBP of \geq 150 and $<$ 160 mmHg, or DBP \geq 90 and $<$ 100 mmHg, OR • Clinically significant increase in DBP of 20 mmHg (but still below 100 mmHg). 	
 • Adjust current or initiate new antihypertensive medication(s). • Titrate antihypertensive medication(s) during the next 2 weeks to achieve well-controlled BP. If BP is not well-controlled within 2 weeks, consider referral to a specialist and go to scenario (B). 	
 • Continue copanlisib at the current dose.
(Scenario B)	
 • Asymptomatic SBP \geq 160 mmHg, or DBP \geq 100 mmHg, OR • Failure to achieve well-controlled BP within 2 weeks in Scenario A. 	
 • Adjust current or initiate new antihypertensive medication(s). • Titrate antihypertensive medication(s) during the next 2 weeks to achieve well-controlled BP. 	
 • Interrupt copanlisib. • Once BP is well-controlled, restart copanlisib at a reduced dose.
(Scenario C)	
 • Symptomatic hypertension OR • Persistent SBP \geq 160 mmHg, or DBP \geq 100 mmHg, despite antihypertensive medication and dose reduction of study treatment 	
 • Adjust current or initiate new antihypertensive medication(s). • Titrate antihypertensive medication(s) during the next 2 weeks to achieve well-controlled BP. • Referral to a specialist for further evaluation and follow-up is recommended. • Continue follow-up per protocol. 	
 • Discontinue copanlisib

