Appendix IV

Dose Modification of Copanlisib for Arterial Hypertension

Toxicity (CTCAE)	Study drug action	Recommendation
Pre-dose measurements BP \geq 150/90 mmHg	No dose should be given until recovery to < 150/90 mmHg.	Consider BP lowering medication. Dosing can proceed on the scheduled day if after at least 2 consecutive measurements BP returns to < 150/90 mmHg. If BP doesn't return to < 150/90 mmHg, delay dosing until next visit.
During infusion: CTCAE hypertension of grade 3 or \geq 160/100 mmHg	Infusion can be interrupted or slowed down and administration of BP lowering therapy should be initiated.	Infusion may be resumed when BP has returned to < 150/90 mmHg at the investigator's discretion or skipped. Subsequent study drug administrations may be reduced by 1 dose level at the investigator's discretion. ^b
Post-dose: Drug-related CTCAE hypertension of grade 3 or \geq 160/100 mmHg ^a	–	Administration of BP lowering therapy should be initiated according to local standard of care. Additional measurements to be performed as clinically indicated until recovery to < 150/90 mmHg. Subsequent study drug administrations may be reduced by 1 dose level at the investigator's discretion. ^b
CTCAE hypertension of grade 4	Permanent discontinuation	–

CTCAE = Common Terminology Criteria for Adverse Events; BP = Blood pressure

^a: Not manageable despite optimal antihypertensive treatment.

^b: The lowest dose level is 30mg.

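### The hypertension dose rules in section 3.5 (scenario table and text) and in Appendix IV give different actions for overlapping situations, and no precedence is stated

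*Protocol*

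**What the plan says.** Three places in the Protocol set the dose action for hypertension.

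- **Section 3.5, Management of Hypertension (text).** For new or worsening hypertension it reads "antihypertensive medication should be initiated or optimized to achieve target blood pressure before interruption or dose reduction of the study treatment at the discretion of", with the investigator named as the one who decides. If hypertension persists despite adequate therapy, the text recommends pausing, lowering the dose or stopping, without choosing among them. Grade 4 requires permanent discontinuation. A first reading in the hypertensive range is repeated at least 2 minutes later and the two are averaged.
- **Section 3.5, scenario table.** Scenario B is triggered by asymptomatic systolic pressure (SBP) of 160 mmHg or more or diastolic pressure (DBP) of 100 or more, or by "Failure to achieve well-controlled BP within 2 weeks in Scenario A". Its action is "Interrupt copanlisib", then "Once BP is well-controlled, restart copanlisib at a reduced dose". Scenario C lists "Symptomatic hypertension OR" persistent values at that level "despite antihypertensive medication and dose reduction of study treatment", and its action is to discontinue. Scenario D discontinues for refractory hypertension or hypertensive crisis.
- **Appendix IV.** The post-dose row covers drug-related hypertension of grade 3 or at least 160/100. Footnote a limits it to hypertension that is "Not manageable despite optimal antihypertensive treatment". The study drug action cell holds only a dash, and the recommendation is that "Subsequent study drug administrations may be reduced by 1 dose level at the investigator's discretion". Footnote b sets 30 mg as the lowest level. Permanent discontinuation appears only in the grade 4 row.

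Section 5.1.11 refers sites to section 3.5 and to Appendix IV without ranking them.

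**The concern.** A site that opens the scenario table finds instructions. A site that reads the preceding text or Appendix IV finds options. Where the triggers overlap, the same patient can be interrupted and reduced, or stopped, under one source and continue under another.

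The accrual goal is 35 patients on one agent. Dose received, time on treatment and the count of discontinuations for toxicity would then partly reflect which page a site followed rather than how the drug was tolerated. For the patient, the protocol does not say whether a given BP requires a change of treatment.

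The point concerns later dosing and discontinuation. It leaves aside how an infusion in progress is handled.

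**Working it through.** The plan gives no figure on this point, so the check sets the three sources side by side.

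**Do the triggers overlap?** Scenario A and the second trigger of Scenario C require persistence, which the table defines as two separate readings during up to three subsequent visits. The first trigger of Scenario B requires neither persistence nor a particular time of measurement, so a post-dose value falls under it. The table also directly follows the treatment-day measurement schedule, which requires readings right after the infusion and 1 h and 2 h later.

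| Situation | Scenario table | Section 3.5 text | Appendix IV |
|---|---|---|---|
| 1a. Asymptomatic, SBP 160 or DBP 100 or more (averaged), responds to treatment | B: interrupt, restart lower | Medication first; interruption or reduction for the investigator to judge | Post-dose row does not apply (footnote a) |
| 1b. Same level, drug-related, post-dose, not controlled by optimal treatment | B: interrupt, restart lower | As 1a; if persistent, one of three actions recommended | No study drug action; one-level reduction optional |
| 2. Recurs at that level despite medication and an earlier dose reduction | C: discontinue (D also, if refractory) | One of three actions recommended | Further one-level reduction optional, floor 30 mg |
| 3. Symptomatic, below grade 4 | C: discontinue, no minimum grade | Symptoms not mentioned; general rules apply | Symptoms not mentioned; optional reduction if the post-dose row applies |
| 4. Grade 4 | No grade-specific row; D discontinues for hypertensive crisis | Permanent discontinuation | Permanent discontinuation |

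- **Rows 1a and 1b.** The table orders what the text leaves to judgement. It also runs interruption and titration together, where the text puts medication first. In 1b Appendix IV adds a third answer.
- **Row 2.** Section 3.5 Table 1 gives 60, 45 and 30 mg. A floor of 30 mg lies two steps below the start, so the optional reduction in Appendix IV can be used again after a first reduction. That is the point at which Scenario C stops treatment.
- **Row 3.** The sources differ only because two of them are silent.
- **Row 4.** There is no conflict.

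The general rule in section 3.5, that interruption for grade 3/4 toxicity is followed by dose reduction, does not resolve this. It applies only once dosing has been interrupted, and whether to interrupt is what the sources dispute.

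**Size for one patient.** First reduction: (60 − 45)/60 = 25%. Second: (45 − 30)/45 = 33%. In row 1 the outcomes run from 60 mg unchanged to interruption and then 45 mg. In row 2, for a patient already at 45 mg, they run from 45 mg unchanged, to 30 mg, to stopping.

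**Size for the trial.** Section 1.3 reports grade 3 hypertension in 19.3% of 57 patients in Study 12871. Applied to the accrual goal of 35: 0.193 × 35 = 6.8, about 7. This does not estimate the number of patients in the conflicting rows. The rate is irrespective of causality, comes from mixed doses in a dose-escalation study, does not separate manageable from unmanageable hypertension, and says nothing about symptomatic hypertension below grade 3.

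**The case against.** The strongest reply is that the scenario table governs BP between visits and Appendix IV governs infusion days, so the two never meet. The Protocol does not say so. Scenario B has no timing condition, the table follows the infusion-day schedule, and the pre-dose row of Appendix IV can postpone a dose to the following visit. This reply also leaves the disagreement between the table and the section 3.5 text.

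Other replies do stand, and they rule out stronger readings that a reader might infer:

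- **One post-dose reading of 162/98 sets all three sources against each other.** It does not. The text averages two readings, and footnote a excludes manageable hypertension from the post-dose row of Appendix IV. For an averaged 162/98 that responds to treatment, only Scenario B and the text conflict.
- **Appendix IV keeps patients with persistently uncontrolled BP on drug.** It does not. Sections 3.1 and 3.5 and the first row of Appendix IV all bar a dose until BP is below 150/90, and section 3.5 takes a patient off treatment after a hold of more than 4 weeks. Row 2 therefore concerns patients whose BP falls below 150/90 before each dose and rises again after it.
- **The section 3.5 text leaves persistent hypertension wholly to discretion.** It does not. It recommends action, and its three options are compatible with Scenarios B and C. It still does not select among them, as the scenarios do.
- **A headache at 155/92 produces a direct contradiction.** The symptom rule can be read as adding to general rules that are silent on symptoms. Scenario C also says discontinue, without the word permanent used for grade 4.

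Appendix IV does not mention a previous reduction, so its optional step could be read as the first one only. The 30 mg floor argues against that reading but does not exclude it.

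**Conclusion.** The contradiction is real and no passage resolves it. It is firmest for asymptomatic SBP of 160 or more or DBP of 100 or more, where Scenario B instructs and the section 3.5 text leaves the choice to the investigator. Appendix IV adds an optional reduction when post-dose hypertension is drug-related and not controlled by optimal treatment. It also holds, more narrowly, for values that recur after each dose despite medication and a reduction already made. For symptomatic hypertension it is an inference from silence. At grade 4 there is no conflict.

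The consequence for an individual ranges from no change, through a 25% lower dose, to stopping treatment. The number affected cannot be derived. About 7 of 35 is at most a rough sign that BP in this range is common; it assumes that the Study 12871 rate carries over to a flat 60 mg, and it should not be read as a count of patients treated inconsistently. The documents do not show which rule was intended, and this review takes no position on that.

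**What to change.** Reconcile the scenario table, the section 3.5 hypertension text and Appendix IV. For each combination of timing (pre-dose, post-dose, between visits), BP level, response to antihypertensive treatment (including whether the dose has already been reduced) and symptom status, state one action and mark it mandatory or discretionary. Keep that statement in one place and have the other passages, including section 5.1.11, refer to it. State explicitly whether Scenario B applies to post-dose values and whether Scenario C's symptom trigger has a minimum grade. The sponsor decides which action applies in each case.

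The cost is a protocol wording amendment and a memo to sites. No visit, measurement or procedure is added.
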